- b: If clinically appropriate and allowed by local regulations, the Week 156 visit can be done by telephone and no labs drawn.
- c: If a flare visit coincides with a scheduled visit, procedures for the scheduled visit should be performed, along with any additional procedures required by a flare visit. Flare visit blood tests are not required if performed within 2 weeks of the Flare visit.
- d: Early termination visits should ideally take place approximately 12 weeks after last study intervention administration, though if a patient intends to withdraw their consent sooner than this milestone the ET visit should be scheduled as needed to accommodate with the patient's intent.
- e: Blood collected from one venipuncture will be divided into multiple aliquots of serum for the measurement of guselkumab concentration, antibodies to guselkumab, and a back-up sample. Details will be provided in the Laboratory Manual.
- f: Ileocolonoscopy does not need to be repeated if an ileocolonoscopy for a flare visit occurred within 12 weeks of the visit date, unless patient and investigator wish to, for example due to subsequent change in clinical status.

Key: AE = adverse event; CD = Crohn's disease; CDAI = Clinical Disease Activity Index; CRP = C-reactive protein; CT = computed tomography; C-SSRS = Columbia Suicide Severity Rating Scale; eCRF = electronic case report form; ET = Early Termination; HBV = hepatitis B virus; HCV = hepatitis C virus; HIV = human immunodeficiency virus; IGRA = interferon gamma release assay; OTC = over the counter; PK = pharmacokinetics; PRO = patient-reported outcome; PROMIS = Patient-Reported Outcomes Measurement Information System; CCI ; TB = tuberculosis; WPAI = Work Productivity Impairment.

Cross Over (CO) Schedule of Activities (Follow if participant meets cross over criteria)

		`		•	Study Visits				
Study Procedure	COp	CO+8 wks	CO+16 wks ^c	Every 16 wks (up to Week 128)	Week 144 - Final Dosing Visit ^e	Week 152 - Final Efficacy Visit ^f	Week 156 -Final Safety Visit ^g	Early Terminati on Visit	Notes
Directed physical exam, with full physical exam where noted (F)	X	X	X	X	X	X(F)		X	Directed physical exam for abdominal mass and fistulas at all visits.
Urine pregnancy test	X	X	X	X	X	X			Must be performed at on-site visits prior to dispensing study intervention in participants of childbearing potential.

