Participants who discontinue study intervention early will return for an early termination visit at least 12 weeks after study intervention discontinuation, which will also serve as their final safety visit. This visit will include a video ileocolonoscopy at the time of discontinuation, except those participants who have already had demonstrated endoscopic recurrence in a study ileocolonoscopy.

Study Length

After the screening period, the total study duration is 156 weeks, with the final dose of study intervention given at Week 144 and the final efficacy visit at Week 152 followed by the final safety visit at Week 156. The end of the study is defined as when all participants have completed the Week 156 visit assessments, or have terminated study participation prior to Week 156 and had their last follow-up assessment (12 weeks after the last dose of study intervention or at early termination visit).

The main study period is defined as when the last randomized participant has completed the Week 48 assessments at which point the main study database lock will occur. Participant follow-up for the main study period may vary depending upon when they enrolled in the trial (estimated to be from 12 to 30 months, based upon an anticipated accrual time of 18 months, but with an upper limit of 36 months [total study treatment duration], should accrual time exceed 18 months).

Endpoints

The primary endpoint is endoscopic recurrence prior to or at Week 48. Video ileocolonoscopy will be performed at the Week 48 visit and centrally read, using a definition of a modified Rutgeerts score of \geq i2a disease activity to define endoscopic recurrence.

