A Week 48 video ileocolonoscopy will be performed between Weeks 48 and 51 and participants with endoscopic recurrence confirmed by a central reader will cross over to open-label treatment with guselkumab SC induction. An optional video ileocolonoscopy can be performed at Week 24 and cross over will occur at the discretion of the principal investigator if there is only endoscopic recurrence without disease recurrence. If participants meet criteria for disease recurrence after Week 8 they will also cross over to open-label treatment.

Participants who discontinue study intervention early will return for an early termination visit at least 12 weeks after study intervention discontinuation, which will also serve as their final safety visit. This visit will include a video ileocolonoscopy at the time of discontinuation, except those participants who have already had demonstrated endoscopic recurrence in a study ileocolonoscopy.

Database Locks and Maintenance of the Blind

The first database lock (DBL) is the main study DBL. It will occur when all participants have completed the Week 48 visit assessments, or have terminated study participation prior to Week 48, and will include all assessments performed as of that date (even those beyond Week 48). The final DBL will occur after the last participant completes the final safety visit at Week 156. Additional DBLs may be added between Weeks 48 and 156, as warranted.

The study blind will be maintained for the investigative sites, site monitors, and study participants until after the final participant has completed their Week 156 visit. In the event of an emergency, the investigator may also unblind a participant's treatment if such knowledge would change the participants' clinical care. The sponsor will remain blinded to the original treatment assignments until after the main study DBL has occurred.

Study Length

After the screening period, the total study duration is 156 weeks, with the final dose of study intervention given at Week 144 and the final efficacy visit at Week 152 followed by the final safety visit at Week 156. The end of the study is defined as when all participants have completed the Week 156 visit assessments, or have terminated study participation prior to Week 156 and had their last follow-up assessment (12 weeks after the last dose of study intervention or at early termination visit).

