1.2.3. Randomization and Blinding

Randomization will be used to minimize bias in the initial assignment of participants to intervention groups, to increase the likelihood that known and unknown participant attributes (eg, demographic and baseline characteristics) are evenly balanced across intervention groups, and to enhance the validity of statistical comparisons across intervention groups. In addition, stratification by known potentially relevant baseline characteristics that may affect study outcomes will also be used to avoid chance imbalance of these relevant variables among treatment groups. Blinded intervention will be used to reduce potential bias during data collection and evaluation of clinical endpoints.

Intervention Allocation

Procedures for Randomization and Stratification

Central randomization will be implemented in this study. At Week 0, participants will be randomly assigned to 1 of 2 intervention groups in a 1:1 ratio based on a computer-generated randomization schedule prepared before the study by or under the supervision of the sponsor. The randomization will be balanced by using randomly permuted blocks and will be stratified by clinical remission status at baseline (CDAI < 150, CDAI \ge 150), region (North America, Western Europe, rest of world) and number of prior surgeries (1 surgery versus > 1 surgery, with the qualifying surgery counting as 1 surgery). The IWRS will assign a unique intervention code, which will dictate the intervention assignment and matching study intervention kit for the participant.

Blinding

To maintain the study blind, the study intervention container will have a label containing the study name, study intervention number, and reference number. The study intervention number will be entered in the eCRF when the study intervention is dispensed. Each active study intervention and its matching placebo will be identical in appearance and will be packaged in identical containers. All participants will receive the same device(s), which could be either active or matching placebo at 8-week intervals to maintain treatment blinding.

The investigator will not be provided with randomization codes. The codes will be maintained within the IWRS, which has the functionality to allow the investigator to break the blind for an individual participant.

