5.7.2. Adverse Events

The verbatim terms used in the CRF by investigators to identify adverse events will be coded using the Medical Dictionary for Regulatory Activities (MedDRA). Any AE occurring at or after the initial administration of study intervention through Week 48 and Week 156, is considered to be treatment emergent. If the event occurs on the day of the initial administration of study intervention, and either event time or time of administration are missing, then the event will be assumed to be treatment emergent. If the event date is recorded as partial or completely missing, then the event will be considered as treatment emergent unless it is known to be prior to the first administration of study intervention based on partial onset date or resolution date. All reported treatment-emergent adverse events will be included in the analysis. For each adverse event, the number and percentage of participants who experience at least 1 occurrence of the given event will be summarized by intervention group. Average duration of study participation follow-up in weeks will be presented for each summary of AEs. The duration of follow-up in weeks will be defined as [(study discontinuation) - (date of first study intervention) + 1]/7 (including the SFU period after the last study intervention), if participants discontinued study intervention prematurely. The duration of follow-up in weeks will be defined as [(date of Visit 48) - (date of first study intervention) + 1]/7, if participants completed study intervention through Week 48. The duration of follow-up in weeks will be defined as [(date of Visit 156) - (date of first study intervention) + 1/7, if participants completed study intervention through Week 156. To account for differences in follow-up times, adverse events will also be summarized using events per 100 participant years of follow-up.

The following summaries will be provided for treatment-emergent adverse events:

- Overall summary of AEs, presenting frequencies and types of AEs
- Summary of AEs by system organ class (SOC) and preferred term (PT)
- Summary of SAEs by SOC and PT
- Summary of related to study intervention AEs (as assessed by the investigator) by system organ class and preferred term
 - A related AE is defined as any event with a relationship to study intervention of 'related' on the AE eCRF page or if the relationship to study intervention is missing.
- Summary of AEs leading to discontinuation of study intervention by SOC and PT

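### SAP 5.7.2 does not cap adverse-event follow-up at each table's cut-off, so Week 48 rates per 100 participant-years can be understated

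*SAP*

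**What the plan says.** SAP 5.7.2 defines the events to be counted in two windows: "Any AE occurring at or after the initial administration of study intervention through Week 48 and Week 156, is considered to be treatment emergent". It promises average follow-up with each adverse-event summary and says that "adverse events will also be summarized using events per 100 participant years of follow-up".

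Three follow-up formulas come next, none of them assigned to either table:

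- **Formula 1** covers people who stop early. It counts from first dose to study discontinuation, "including the SFU period after the last study intervention), if participants discontinued study intervention prematurely".
- **Formula 2** counts to Visit 48: "date of Visit 48) - (date of first study intervention) + 1]/7, if participants completed study intervention through Week 48".
- **Formula 3** counts to Visit 156 for people who completed study intervention through Week 156.

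On timing, Protocol 4.1 describes the study "with the final dose of study intervention given at Week 144". The Protocol 1.3 footnote on early termination reads "Early termination visits should ideally take place approximately 12 weeks after last study intervention administration". SAP 1.2.1 says that early stoppers "will return for an early termination visit at least 12 weeks after study intervention discontinuation, which will also serve as their final safety visit". Dosing follows a common schedule, "which could be either active or matching placebo at 8-week intervals to maintain treatment blinding" (SAP 1.2.3). Under SAP 1.2.1 the main lock also takes in data from after Week 48.

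SAP Section 1 states that the trial ended with four participants, that the planned analyses no longer apply, and that they are printed for reference.

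**The concern.** A rate per participant-year needs events and time from the same window. In the Week 48 table the events stop at Week 48, but formula 1 does not. Any time it adds beyond Week 48 enlarges the denominator without allowing events into the numerator, so the error can only lower the rate.

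There are two routes to excess time:

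- A participant who stops shortly before Week 48 may have the early termination visit after it.
- A participant who completes Week 48 and stops later fits formulas 1 and 2 at once. Someone who stops at Week 80 and leaves at Week 92 has 92 weeks under formula 1 and 48 under formula 2. Two programmers could choose differently, and both would be following the text.

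Formula 3 has a separate wording fault. With the last dose at Week 144, nobody literally completes study intervention through Week 156.

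The participant-year rate is the SAP's own adjustment for unequal follow-up, so its denominator ought to be unambiguous.

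**Working it through.** The documents give no adverse-event rate or participant-year total, so there is no plan figure to reproduce for this point. One input can be checked. With accrual of 25%, 35% and 40% in successive six-month periods and a lock at 30 months (SAP Section 3), mean available follow-up is 30 − (0.25×3 + 0.35×9 + 0.40×15) = 20.1 months. This agrees with the stated average of about 20 months.

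**Inputs**

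- Dosing every 8 weeks, so the doses before Week 48 fall at Weeks 0, 8, 16, 24, 32 and 40.
- Study exit 12 weeks after the last dose (A, Protocol 1.3) or 12 weeks after the stopping date (B, SAP 1.2.1). For the second reading below, exit on the stopping date is added as a lower bound.
- Stopping treatment at 15% a year with a constant hazard. The 15% is the dropout figure in SAP Section 3, and using it as the stopping rate is an assumption. Range tried: 5% to 30%.

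Understatement = 1 − (mean follow-up capped at Week 48) / (mean follow-up under the SAP rule), with the same event count.

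**Who passes Week 48 among those who stop before it?** Under A, last doses at Weeks 0, 8, 16, 24, 32 and 40 give exits at Weeks 12, 20, 28, 36, 44 and 52. Only the last slot passes Week 48, by 4 weeks.

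**Reading 1: formula 2 governs everyone who completes Week 48.**

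- Stopping before Week 48: 1 − 0.85^(48/52) = 13.9%.
- A: stopping between Weeks 40 and 48 is 0.85^(40/52) − 0.85^(48/52) = 0.8825 − 0.8607 = 2.2%. Excess 0.0218 × 4 = 0.087 weeks. Mean follow-up is 45.69 weeks against 45.60 capped, an understatement of 0.2%.
- B: stopping between Weeks 36 and 48 is 3.3%, with a mean excess of about 6 weeks. Mean follow-up is 46.24 weeks against 46.05 capped, an understatement of 0.4%.

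**Reading 2: formula 1 also governs those who complete Week 48 and stop later, with data available at the main lock.** By simulation, 9.7% of participants stop after Week 48 and before the lock.

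| Study exit | Capped mean (weeks) | SAP mean (weeks) | Understatement at 15% | At 5% to 30% |
|---|---|---|---|---|
| On stopping date | 44.58 | 46.97 | 5.1% | 1.9% to 8.5% |
| A: last dose + 12 weeks | 45.60 | 48.79 | 6.5% | 2.5% to 10.7% |
| B: stopping date + 12 weeks | 46.05 | 49.63 | 7.2% | 2.8% to 11.8% |

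For reading 1 the range over 5% to 30% is 0.07% to 0.38% (A) and 0.15% to 0.83% (B).

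**The case against.** The best defence is that the formulas are meant to be read table by table. SAP 5.2 sets completing study intervention through Week 48 beside discontinuing it before Week 48. If the Week 48 table follows that split, stopping prematurely means stopping before Week 48, formula 2 covers all later stoppers, and the effect is below 1%. This is a fair reading and may well be the intended one. The text does not settle it, however. Protocol 4.4 uses the same idea of premature stopping for anyone who stops before the Week 144 dose, which would bring a Week 80 stopper under formula 1. Even on the favourable reading, a last dose at Week 40 followed by the scheduled exit at about Week 52 leaves time in the denominator that should not be there.

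It is also fair that the participant-year rate is an additional display. The main summaries are percentages of participants with an event, and the formula does not touch them.

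A reader might draw four stronger conclusions, which the documents do not support:

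- **Every early stopper is over-counted.** The missing cap applies to all of them, but at 15% about 76% to 84% of those who stop before Week 48 also leave by Week 48. Their safety follow-up time is properly counted.
- **Completers' rates in the Week 156 table are inflated about threefold (156/48 = 3.25).** This requires giving a full completer the Visit 48 date because formula 3's condition cannot literally be met. Formula 3 names Visit 156, and SAP 5.2 uses similar shorthand for Week 156, so the intent is clear.
- **The understatement reaches about 20%.** This needs the Week 48 table to be rerun on final data with formula 1 overriding formula 2. No such rerun is planned.
- **The rule hides or creates a difference between arms.** Unequal stopping would give unequal understatement, but the documents project no arm-specific stopping rates for this trial, so nothing can be claimed about size or direction.

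**Conclusion.** The point holds as a faulty denominator rule, usually of small effect. Formula 1 has no cut-off, its overlap with formula 2 is unresolved, and formula 3's condition cannot be met as worded. At 15% a year the understatement of Week 48 rates is about 0.2% to 0.4% if formula 2 governs Week 48 completers (under 1% across 5% to 30%). It is about 5% to 7% at the main lock if formula 1 governs them (about 2% to 12% across 5% to 30%). The SAP does not say which applies, so it cannot be said flatly that the rates are understated, only that they can be.

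These sizes rest on a constant stopping hazard, on dropout standing in for stopping treatment, and on exit no later than 12 weeks after stopping. SAP 1.2.1 says at least 12 weeks, so the excess could be somewhat larger.

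With four participants enrolled, no such rate is due to be reported. The defect matters for the reference plan and for any reuse of this wording.

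**What to change.** Replace the three conditional formulas with one definition applied separately to each table:

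follow-up in weeks = [earliest of (study discontinuation or last study contact; the table's cut-off visit, Week 48 or Week 156; data cut-off) − date of first study intervention + 1] / 7.

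This supplies the cap, removes the overlap and drops the unreachable Week 156 condition. It keeps safety follow-up time that falls inside the window, as it should.

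The cost is a change of SAP wording and the matching derivation. No new data are needed, and the percentages of participants with an event stay the same.

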5.7.3. Additional Safety Assessments

5.7.3.1. Clinical Laboratory Tests

The following laboratory tests will be performed during the study and summaries will be provided:

Laboratory Assessments	Parameters				
Hematology	Platelet count Red blood cell count Hemoglobin Hematocrit	RBC Indices: MCV MCH % Reticulocytes	White Blood Cell (WBC) count with Differential: Neutrophils Lymphocytes Monocytes Eosinophils Basophils		
	laboratory. A RBC evaluation	include any abnormal cells, whi may include abnormalities in the vill then be reported by the labor r will also be reported.	e RBC count, RBC parameters,		

Protocol-Required Safety Laboratory Assessments

Statistical Analysis Plan CNTO1959CRD3007

Laboratory	Parameters				
Assessments					
Clinical	Sodium	Total bilirubin			
Chemistry	Potassium	Alkaline phosphatase			
	Chloride	Calcium			
	Bicarbonate	Phosphate			
	Blood urea nitrogen (BUN)	Albumin			
	Creatinine	Total protein			
	Glucose [nonfasting]	Magnesium			
	Aspartate aminotransferase (AST)/Serum				
	glutamic-oxaloacetic				
	Alanine aminotransferase (ALT)/Serum				
	glutamic-oxaloacetic				
	Gamma-glutamyltransferase (GGT)				
	Note: Details of liver chemistry stopping criteria	and required actions and follow-up are given			
	in Appendix 13: Liver Safety.				
	A possible Hy's law Case is defined by the occurrence of ALT/AST \geq 3 x ULN, alkaline phosphatase (ALP) <2 x ULN together with total bilirubin \geq 2 x ULN or International Normalized Ratio (INR) >1.5 (if measured). Any possible Hy's Law case is considered an important medical event and must be reported to the sponsor in an expedited manner, even before all other possible causes of liver injury have been excluded. A confirmed Hy's law case must be reported as a SAE.				
Other Screening Tests	• Serum (at screening) and urine Pregnancy 7 only)	Testing (for women of childbearing potential			
	• Serology (at screening; HIV antibody, hepatitis B surface antigen [HBsAg], and hepatitis C virus antibody, hepatitis B surface antibody [antiHBs], hepatitis B core antibody total [anti-HBc])				
	• TB evaluation (QuantiFERON-Gold)				

Clinical laboratory test values are to be graded based on National Cancer Institute Common Terminology Criteria for Adverse Events (NCI-CTCAE) version 5.0 (Protocol Attachment 10). The laboratory tests not included in NCI-CTCAE tables in Attachment 10 will not be presented in the corresponding tables or listings.

Summaries of clinical laboratory tests by study intervention group over time will be provided for participants in the Safety Analysis Set:

- Summary of maximum NCI-CTCAE toxicity grade for post-baseline laboratory values through Week 48 and through Week 156.
- Shift tables for maximum NCI-CTCAE toxicity grade from baseline through Week 48 and through Week 156 will be summarized for the following lab parameters:
 - Hematology: hemoglobin, platelets, total WBC, absolute lymphocytes, and absolute neutrophils;
 - Chemistry: ALT, AST, alkaline phosphatase, and total bilirubin.
- Summary of maximum post-baseline measurement through Week 48 and through Week 156 for ALT, AST, alkaline phosphatase, and total bilirubin relative to ULN.

CONFIDENTIAL – FOIA Exemptions Apply in U.S.

- Summary of maximum post-baseline measurement through Week 48 and through Week 156 for ALT, AST, alkaline phosphatase, and total bilirubin relative to ULN among participants taking immunomodulators at baseline.
- Summary of maximum post-baseline elevated liver function tests through Week 48 and through Week 156 by the following categories for ALT, AST, alkaline phosphatase, and total bilirubin relative to ULN:
 - > 1 to \leq 3 x ULN
 - > 3 to \leq 5 x ULN
 - > 5 to \leq 10 x ULN
 - > 10 to \leq 20 x ULN
 - > 20 x ULN
- Summary of potential Hy's Law case (ALT or AST \ge 3 x ULN and total bilirubin \ge 2 x ULN or INR >1.5) through Week 48 and through Week 156.
- Box plots of observed laboratory values and change from baseline in laboratory parameters (hematology and chemistry) through Week 48 and through Week 156 will be provided.

Listings of participants with any abnormal post-baseline laboratory values of NCI-CTCAE grade ≥ 2 , participants with maximum post-baseline elevated liver function tests (AST or ALT >5xULN) and participants with potential Hy's Law case (ALT or AST $\geq 3 \times$ ULN and total bilirubin $\geq 2 \times$ ULN or INR >1.5), will also be provided by study intervention group, participant, and visit.

There will be no imputation for missing laboratory values.

Any laboratory values given as <X.X in the database will be imputed with the value of the number without the sign for the descriptive statistics and the calculation of changes from baseline, eg. a value of <2.2 will be imputed as 2.2 for the calculations.

